Study TAK-831-1005 is an ongoing, investigator- and subject-blinded, sponsor-unblinded, placebo-controlled study designed to continue evaluation of the safety, tolerability, PK, and pharmacodynamics (PD) of escalating multiple (OD) doses of TAK-831 in healthy subjects at doses higher than those achieved in Study TAK-831-1001. The following data from this study are preliminary, being based on blinded AE data reported by the investigator and blinded safety endpoint data. Although not expected, these data are subject to change upon finalization following study monitoring, source data verification, and discrepancy query management before database lock. As of the cut-off date of 18 September 2017, 2 cohorts of 8 subjects each (6 TAK-831:2 placebo) have completed dosing with TAK-831 600 mg QD (T2 tablets). TAK-831 800 mg QD (oral suspension) or placebo, administered first as a single dose and then QD for up to 14 days. In addition to standard safety assessments, subjects underwent catheterized cerebrospinal fluid (CSF) collection for a 24-hour period starting before dosing on Day 1 of single-dose treatment and on Day 14 of multiple-dose treatment. Nausea and postlumbar puncture syndrome were the most commonly reported TEAEs; nausea in the absence of postlumbar puncture syndrome was reported by 1 subject in each cohort. All episodes of nausea were mild in intensity and self-limiting. Two subjects in each cohort met the criteria for orthostatic hypotension on at least 1 assessment; none of these findings were associated with a TEAE of dizziness. No concerning trends in clinical laboratory, ECG, or vital sign data were observed for these cohorts.

Following QD dosing, mean plasma exposures of TAK-831 were higher (C_{max} : 1.3-fold and area under the plasma concentration-time curve [AUC]: 1.8-fold) when dosed as an oral suspension

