- Eosinophilic intranuclear inclusion bodies (EIIBs) were observed in the proximal tubule epithelium of the kidneys at doses of ≥10 mg/kg/day in rats. The EIIBs were not accompanied by apparent necrosis, inflammation, or impaired renal function and were not considered adverse. Similar findings have been reported in the literature and are considered to be species-specific to the rat [19]. Elevated creatinine levels were not reported in the TAK-831 clinical studies summarized above; creatinine will continue to be measured in the clinical studies.
- Postural hypotension and dizziness were observed in prior TAK-831 studies in healthy subjects. However, the incidence of dizziness in subjects treated with TAK-831 and placebo was similar. Subjects will be informed of these findings and possible ways to mitigate this risk, and orthostatic vital sign assessments will be monitored periodically at study visits.
- Study procedure–specific risks include issues relating to blood collection for safety assessment/PK monitoring (venipuncture may cause discomfort at the site of puncture; bruising and swelling; and rarely, infection or faintness from the procedure), and the placement of ECG pads, which may cause some local redness and/or erythema/itching. The PD assessments planned for the study, aside from those requiring a blood draw, are noninvasive and are associated with minimal risk.

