- 26. The subject has type 1 diabetes that requires insulin for their treatment; has type 2 diabetes that is poorly controlled; has had changes to their diabetic treatment regimen within 30 days before screening; or has had hospitalizations for diabetes and/or diabetes-related conditions in the past 6 months before screening. As an exception, subjects who have consistently demonstrated the ability to adhere to their insulin and dietary regimens for an extended period of time in addition to demonstrating stable control of type 2 diabetes mellitus for an extended period of time may be considered for enrollment after discussion with the sponsor or designee.

- 27. The subject has 1 or more laboratory values outside the normal range that are considered by the investigator to be clinically significant at the screening visit.
- 28. The subject has any of the following at the screening visit: a serum creatinine value >1.5 × upper limit of normal (ULN); a serum total bilirubin value >1.5 × ULN; a serum alanine aminotransferase (ALT) or aspartate aminotransferase (AST) value >2 × ULN. As an exception, subjects with Gilbert syndrome may be considered for enrollment after discussion with the sponsor or designee if the direct bilirubin is within the normal range. Subjects with a positive hepatitis B surface antigen (HBsAg) test result, or known or suspected active hepatitis C infection are also excluded.
- 29. The subject does not have a stable residence or is homeless.

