10.1.3 Additional Points to Consider for PTEs and AEs

An untoward finding generally may:

- Indicate a new diagnosis or unexpected worsening of a pre-existing condition. (Intermittent events for pre-existing conditions or underlying disease should not be considered PTEs or AEs.)
- Necessitate therapeutic intervention.
- Require an invasive diagnostic procedure.
- Require discontinuation or a change in dose of study drug or a concomitant medication.
- Be considered unfavorable by the investigator for any reason.
- PTEs/AEs caused by a study procedure (eg, a bruise after blood draw) should be recorded as a PTE/AE.

Diagnoses versus signs and symptoms:

• Each event should be recorded to represent a single diagnosis. Accompanying signs (including abnormal laboratory values or ECG findings) or symptoms should NOT be recorded as additional AEs. If a diagnosis is unknown, sign(s) or symptom(s) should be recorded appropriately as a PTE(s) or AE(s).

Laboratory values and ECG findings:

- Changes in laboratory values or ECG findings are only considered to be PTEs or AEs if they are judged to be clinically significant (ie, if some action or intervention is required or if the investigator judges the change to be beyond the range of normal physiologic fluctuation). A laboratory or ECG retest and/or continued monitoring of an abnormal value or finding are not considered an intervention. In addition, repeated or additional noninvasive testing for verification, evaluation, or monitoring of an abnormality is not considered an intervention.
- If abnormal laboratory values or ECG findings are the result of pathology for which there is an overall diagnosis (eg, increased creatinine in renal failure), the diagnosis only should be reported appropriately as a PTE or AE.

Pre-existing conditions:

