7.12.2 Clinical Laboratory Evaluations

Clinical laboratory tests will be assessed using the Safety Set and will be evaluated and presented using International System of Units (SI) units unless otherwise stated. Refer to Protocol Section 9.1.10 as well as the schedule of the events for a list of all clinical laboratory tests.

All laboratory test parameters will be displayed in individual subject data listings in both SI units and conventional (CV) units. For test results not in SI units, the conversion to SI units will be done in the derived Study Data Tabulation Model (SDTM) and Analysis Data Model (ADaM) datasets using the known conversion factors. If necessary, SI units from the central laboratory may be converted to Takeda's preferred SI units in the derived SDTM and ADaM datasets. All summaries and analyses will be based on the values using these preferred SI units.

Only observations within 3 days of the last dose of study drug will be included in the tables. No inferential statistics will be presented unless otherwise stated.

Descriptive statistics (N, mean, SD, median, minimum, and maximum) for the observed and change from baseline values will be presented. Study baseline will be used for change from baseline. Note that "character" urinalysis tests will only be listed.

Laboratory markedly abnormal values (MAVs), identified by the criteria defined in Appendix A, will be tabulated. If a subject has a MAV for a particular laboratory test, all visits for that subject for that parameter will be listed. The number and percentage of subjects with at least 1 postdose markedly abnormal laboratory test result will be summarized. The mapping of the subjects who meet the MAV criteria will be listed as a table. All observations, including ones at unscheduled visits, will be included in the MAV evaluation and summaries.

Listings of all clinical safety laboratory data will be provided in Appendix 16.2 and will be presented in both SI and CV units. Laboratory data outside of the normal reference range will be indicated in the listings. In addition, MAVs will be flagged. The listing will include site number, subject identifier, age, gender, treatment group, study visit, and sample collection date.

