7.14 Changes in the Statistical Analysis Plan

Considering the potential impact of noncompliant subjects, a supportive analysis on the primary endpoint based on PPS described in section 7.9.1 is added.

Section 7.2.5 is updated to provide details on site pooling method.

A separate listing for protocol deviations due to COVID-19 is added.

In section 7.9.2, clarification is added to describe the analyses on BNSS total (12-item, excluding item 4) and BNSS total (13-item).

Typographical errors are corrected.

Appendix A Criteria for Identification of Markedly Abnormal Laboratory Values Hematology—Criteria for Markedly Abnormal Values

Parameter	Unit	Low Abnormal	High Abnormal
Hemoglobin	Both	$< 0.8 \times LLN$	> 1.2 × ULN
Hematocrit	Both	$< 0.8 \times LLN$	> 1.2 × ULN
RBC count	Both	$< 0.8 \times LLN$	> 1.2 × ULN
WBC count	Both	<0.5 x LLN	>1.5 x ULN
Platelet count	Conventional	$<75 \text{ x } 10^{3}/\mu\text{L}$	>600 x 10 ³ /µL
	SI	<75 x 10 ⁹ /L	>600 x 10 ⁹ /L

LLN=lower limit of normal, RBC=red blood cell, ULN=upper limit of normal, WBC=white blood cell.

Serum	Chemistry-	Criteria	for Ma	rkedly	Abnormal	Values
	•/			•		

Parameter	Unit	Low Abnormal	High Abnormal
ALT	Both		>3x ULN
AST	Both		>3x ULN
GGT	Both		>3x ULN
Alkaline phosphatase	Both		>3x ULN
Total bilirubin	Conventional		>2.0 mg/dL
	SI		>34.2 µmol/L
Albumin	Conventional	<2.5 g/dL	
	SI	<25 g/L	
Total protein	Both	<0.8x LLN	>1.2x ULN
Creatinine	Conventional		>2.0 mg/dL
	SI		>177 μmol/L
Blood urea nitrogen	Conventional		>30 mg/dL
	SI		>10.7 mmol/L
Sodium	Conventional	<130 mEq/L	>150 mEq/L
	SI	<130 mmol/L	>150 mmol/L
Potassium	Conventional	<3.0 mEq/L	>6.0 mEq/L
	SI	<3.0 mmol/L	>6.0 mmol/L
СРК	Both		>5x ULN
Glucose	Conventional	< 50 mg/dL	>350 mg/dL
	SI	< 2.8 mmol/L	>19.4 mmol/L

ALT=alanine aminotransferase, AST=aspartate aminotransferase, CPK=creatine phosphokinase, GGT=γ-glutamyl transferase, LLN=lower limit of normal, ULN=upper limit of normal.

Parameter	Unit	Lower Criteria	Upper Criteria
Pulse	bpm	<50	>120
Systolic blood pressure	mm Hg	<85	>180
Diastolic blood pressure	mm Hg	<50	>110
Body temperature	°C	< 35.6	>37.7

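### Creatinine is counted by arm only above a fixed 2.0 mg/dL, so a large rise from baseline that ends at or below that value is in no by-arm creatinine count

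*SAP*

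**What the plan says.** SAP 7.12.2 defines the laboratory safety count by reference to a table: "Laboratory markedly abnormal values (MAVs), identified by the criteria defined in Appendix A, will be tabulated". The number and percentage of subjects with at least one postdose markedly abnormal value (MAV) are then summarised, with unscheduled visits included.

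The table is headed "Appendix A Criteria for Identification of Markedly Abnormal Laboratory Values Hematology—Criteria for Markedly Abnormal Values" and continues with serum chemistry. It has 5 hematology and 13 chemistry parameters. Creatinine has one limit, above 2.0 mg/dL (above 177 umol/L). None of the 18 parameters has a limit relative to the subject's own baseline.

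Two other laboratory outputs are planned:

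- Summaries: "Descriptive statistics (N, mean, SD, median, minimum, and maximum) for the observed and change from baseline values will be presented".
- Listings: "Laboratory data outside of the normal reference range will be indicated in the listings".

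Neither SAP 7.12.2 nor Protocol 13.1.7.2 plans a laboratory shift table or a count of subjects by size of rise. The ECG plan has both kinds of output. SAP 7.12.4 plans shift tables for the ECG interpretation, and the QTc criteria include an option that pairs a change of at least 30 ms from baseline with a value of at least 450 ms.

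Protocol 4.3 describes inclusion bodies in the kidney tubules of rats and ends that item by saying that "creatinine will continue to be measured in the clinical studies".

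**The concern.** Creatinine is the analyte that Protocol 4.3 names for continued follow-up of an animal kidney finding. A table that counts subjects by arm is where one would look for a drug-related pattern, and for creatinine that table responds only to values above 2.0 mg/dL. For a subject starting at 0.8 mg/dL, creatinine can double without being counted.

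The remaining outputs do not supply the missing count. The SD and maximum of change can show that some subject rose sharply, but not how many did in each arm. The listings hold the data, but a count from them would be made by hand, with a cut-off chosen after unblinding. The adverse event route depends on judgement. Under Protocol 10.1.3 a laboratory change qualifies if some action is required "or if the investigator judges the change to be beyond the range of normal physiologic fluctuation", and a retest or continued monitoring is not an action. ALT and AST have fixed reporting and stopping rules (Protocol 7.6 and 10.2.3); we found none for creatinine.

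Exposure is also longer than before. Dosing lasts 84 days here. In the most recent multiple-dose study described in Protocol 4.1.3, drug was "administered first as a single dose and then QD for up to 14 days".

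**Working it through.** **1. The plan's own figure.** With the molar mass of creatinine (113.12 g/mol, a physical constant not in the documents), 1 mg/dL = 10,000/113.12 = 88.40 umol/L. So 2.0 mg/dL = 176.8, which rounds to 177 umol/L. The two stated limits agree.

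**2. Fold rise needed.** This is 2.0 divided by baseline: 2.0/0.8 = 2.50, 2.0/1.0 = 2.00, 2.0/1.2 = 1.67. The value must exceed 2.0 to count, so the rule misses an exact doubling from any baseline up to 2.0/2 = 1.0 mg/dL. It misses an exact 1.5-fold rise from any baseline up to 2.0/1.5 = 1.33 mg/dL. The example 0.8 to 1.9 is 1.9/0.8 = 2.4-fold and is not counted.

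**3. What the summary statistics show.** Suppose 3 of 52 subjects in one arm go from 0.8 to 1.6 mg/dL.

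- Creatinine MAV count: 0 of 52.
- Shift in the arm mean: 3 × 0.8/52 = 0.046 mg/dL.
- SD of change = √(s² + 0.64 p(1 − p)), with s = √2 × 0.85 × CV (assumed mean 0.85 mg/dL, within-subject CV 6% to 12%), so s = 0.072 to 0.144. With p = 3/52 the SD is 0.20 to 0.24; with p = 1/52 it is 0.13 to 0.18.

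The spread is visible, but the number of subjects is not. A count at 1.5 times baseline and above ULN would read 3 of 52 (5.8%), provided the ULN is below 1.6.

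**4. Share of true k-fold rises counted.** The documents give no baseline distribution and no ULN. Assume normal baselines b with mean 0.75 to 0.95 and SD 0.15 to 0.20 mg/dL, and ULN 1.0 to 1.2 mg/dL. The fixed rule counts P(b > 2.0/k). The added rule counts P(b > ULN/k), because any rise of 2-fold or more already meets the 1.5-fold part. The ranges cover every combination of these limits.

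| True rise | Fixed rule, above 2.0 | Added rule |
|---|---|---|
| 2-fold | 5% (mean 0.75, SD 0.15) to 40% (0.95, 0.20) | 77% (0.75, 0.20, ULN 1.2) to nearly 100% |
| 2.5-fold | 37% (0.75, 0.15) to 84% (0.95, 0.15) | 91% (0.75, 0.20, ULN 1.2) to nearly 100% |

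**5. Chance flags from the added rule.** Simulated subjects had no true change, lognormal within-subject error on baseline and on each visit, and the same baseline and ULN ranges. Three post-baseline visits are scheduled (Days 28, 56 and 84/ET). The probability of a flag per subject is essentially 0 at a CV of 6% and at most about 0.019 at 12%. That gives 52 × 0.019 = 1.0 per active arm and 234 × 0.019 = 4.4 overall. With one extra unscheduled sample per subject the maximum is about 0.024, giving 52 × 0.024 = 1.2 and 234 × 0.024 = 5.6.

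**The case against.** The strongest reply is that nothing here is wrong. The protocol's safety endpoint is the percentage of subjects meeting the sponsor's markedly abnormal criteria, and the SAP delivers exactly that. An extra row is a preference. This stands: there is no contradiction and nothing that cannot be computed.

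A reader might infer that a kidney signal could pass unseen. The documents do not support that. Appendix A has a second renal row, blood urea nitrogen above 30 mg/dL. Change from baseline is summarised with its maximum, out-of-range values are marked in listings that show treatment group, and a rise reported as an adverse event is tabulated by arm. An internal data monitoring committee reviews unblinded safety data (Protocol 11.1). What is missing is a prespecified creatinine count by arm, not sight of the data.

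A reader might also infer that Protocol 4.3 treats the kidney as a known risk. It says that the rat finding came without impaired renal function, was not considered adverse and is regarded as specific to the rat. It adds that elevated creatinine was not reported in the clinical studies it summarises. This limits the weight of the point.

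A third inference is that the fixed limit treats subjects unevenly, because exclusion 28 admits screening creatinine up to 1.5 times ULN and such a subject would need only a small further rise. Exclusion 27 removes out-of-range laboratory values judged clinically significant, and exclusion 2 removes uncontrolled, clinically significant renal disease. Such entrants are likely few, so this argument is not relied on.

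Finally, the added row would carry noise. That stands, and it limits how small counts can be read.

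**Conclusion.** The point holds as a modest gap in safety reporting. A creatinine rise as large as 2.4-fold from 0.8 mg/dL falls in no by-arm creatinine count, for an analyte that the protocol itself names for follow-up. That part rests on the text alone.

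The size rests on assumed baselines, ULN and within-subject variation, none of which the documents give. The capture percentages show how the two rules behave; they do not predict what this trial will find. Efficacy conclusions and the MAV safety endpoint are not affected.

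**What to change.** Keep the creatinine MAV row and the MAV safety endpoint unchanged. Add one sentence to SAP 7.12.2 for a supplementary by-arm count: subjects with at least one postdose creatinine of at least 1.5 times baseline and above ULN, using the same observations as the MAV summary. This pairs a change with an absolute level, as the QTc criteria already do. The 1.5 multiple is a proposal, not a figure from the documents.

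Both rows are needed. A rise from 1.8 to 2.1 mg/dL (1.17-fold) is caught only by the MAV row, and a rise from 0.8 to 1.9 only by the new one (if the ULN is below 1.9).

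The cost is one sentence and one table row from samples already scheduled. The downside is the chance flags worked out above. A count of one or two in an arm should not be taken as a signal without looking at the placebo arm and the individual profiles.

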7.12.3 Vital Signs

Descriptive statistics (N, mean, SD, median, minimum, and maximum) will be used to summarize vital sign parameters at baseline, each post-baseline visit, and change from baseline to each post-baseline visit. Only observations within 3 days of the study drug will be included in the tables.

Vital sign MAVs, identified by the criteria defined in Appendix B, will be tabulated. If a subject has a MAV for a particular vital signs parameter, all visits for that subject for that parameter will be listed. The number and percentage of subjects with at least 1 postdose markedly abnormal vital signs measurement will be summarized. The mapping of the subjects who meet the MAV criteria will be listed as a table. All observations, including ones at unscheduled visits, will be included in the MAV evaluation and summaries.

Orthostatic hypotension, identified by the criteria defined in Appendix C, will be calculated at every time point where standing and supine measurements are available using the formula: standing vital measurement – supine vital measurement. The mapping of the subjects who meet the criteria for orthostatic hypotension will be listed by study visit as a table. All orthostatic hypotension observations, including ones at unscheduled visits, will be included in the subject mappings.

Listings of all vital signs data will be provided in Appendix 16.2. Vital sign MAVs will be flagged in the listings. The listing will include site number, subject identifier, age, gender, treatment group, study visit, and sample collection date.

7.12.4 12-Lead ECGs

Descriptive statistics (N, mean, SD, median, minimum, and maximum) of ECG parameters, including heart rate, PR interval, RR interval, QRS interval, QT interval, and QTc interval (Fredericia's and Bazett's corrections), will be presented for baseline, each post-baseline visit, and change from baseline to each post-baseline visit. Only the scheduled measurements will be included in the summary. Only observations within 3 days of the study drug will be included in the tables. No inferential statistics will be presented.

ECG MAVs, identified by the criteria defined in Appendix D, will be tabulated. If a subject has a MAV for a particular 12-lead ECG parameter, all visits for that subject for that parameter will be listed. The number and percentage of subjects with at least 1 postdose markedly abnormal 12-lead ECG measurement will be summarized. The mapping of the subjects who meet the MAV criteria will be listed as a table. All observations, including ones at unscheduled visits, will be included in the MAV evaluation and summaries.

Overall ECG interpretation category (normal, abnormal not clinically significant, abnormal clinically significant) is collected by eCRF at baseline and at each scheduled post-baseline visit. Shifts in ECG interpretation will be presented as cross-tabulations (baseline versus each post-baseline visit) of numbers of subjects with normal, abnormal not clinically significant, and abnormal clinically significant interpretations with missing, if applicable, and total categories by regimen.

TAK-831-2002	Page 24 of 30
Statistical Analysis Plan Amendment No. 1	01 February 2021

Listings of all 12-lead ECG data will be provided in Appendix 16.2. MAVs will be flagged in the listings. The listing will include site number, subject identifier, age, gender, treatment group, study visit, and sample collection date.

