- 20. The subject has received TAK-831 in a previous clinical study; or has previously or is currently participating in this study; has received treatment with other experimental therapies within the preceding 60 days or <5 half-lives prior to randomization, whichever is longer; has participated in 2 or more clinical studies within 12 months prior to screening; or has participated in a clinical study for a psychiatric condition that is exclusionary per this protocol.
- 21. The subject is known by history or subject reporting to be currently infected or to have been infected with human immunodeficiency virus (HIV).
- 22. The subject has a known hypersensitivity to any component of the formulation of TAK-831 or to the practice pills (ie, small candies) used during the compliance monitoring device training.
- 23. The subject has a history of cancer. As an exception, subjects may be enrolled if they have a history of treated basal cell carcinoma, stage I squamous cell skin cancer, or in situ cervical cancer that has been in remission for ≥5 years prior to first dose of study drug.
- 24. Subjects with evidence or history of current clinically significant cardiovascular disease, including uncontrolled hypertension (supine diastolic blood pressure >95 mm Hg and/or supine systolic blood pressure >160 mm Hg, with or without treatment), symptomatic ischemic heart disease, uncompensated heart failure or recent (past 12 months) acute myocardial infarction or bypass surgery. Controlled essential hypertension and nonclinically significant sinus bradycardia and sinus tachycardia will not be considered significant medical illnesses and would not exclude a subject from the study.
- 25. The subject has a QT interval with Fridericia correction method (QTcF) >450 msec (males) or >470 msec (females), confirmed with 1 repeat testing, at screening or Day 1, or the subject has long QT syndrome or is under the treatment with Class 1A (eg, quinidine, procainamide) or Class 3 (eg, amiodarone, sotalol) antiarrhythmic drugs.

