5.1.3 Safety Endpoints

- Percentage of subjects who experience at least 1 TEAE.
- Percentage of subjects who meet the markedly abnormal criteria for safety laboratory tests at least once postdose.
- Percentage of subjects who meet the markedly abnormal criteria for vital sign measurements at least once postdose.
- Percentage of subjects who meet the markedly abnormal criteria for safety electrocardiogram (ECG) parameters at least once postdose.
- Percentage of subjects with treatment-emergent suicidal ideation or suicidal behavior as measured using the C-SSRS.

TAK-831-2002 Statistical Analysis Plan Amendment No. 1

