Appendix B Criteria for Abnormal Changes from Baseline of Vital Signs

Appendix C Criteria for Identification of Markedly Abnormal Orthostatic Changes

Parameter	Criteria
Orthostatic Hypotension	(Orthostatic Systolic Blood Pressure < -20 mm Hg OR
	Orthostatic Diastolic Blood Pressure < -10 mm Hg) AND Heart Rate Increase > 20 beats/min

Note: Orthostatic measurement = standing vital measurement – supine vital measurement.

Parameter	Lower Criteria	Upper Criteria
Heart rate	< 50 beats per minute	>120 beats per minute
PR	≤80 milliseconds	≥200 milliseconds
QT Interval	≤300 milliseconds	≥460 milliseconds
QTcB Interval	≤300 milliseconds	≥500 milliseconds OR
		≥30 milliseconds change from baseline and ≥450 milliseconds
QTcF Interval	≤300 milliseconds	≥500 milliseconds OR
		≥30 milliseconds change from baseline and ≥450 milliseconds
QRS	≤80 milliseconds	≥180 milliseconds

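### The markedly abnormal value counts do not separate abnormalities already present at baseline, and the SAP gives two conflicting rules on off-drug values

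*SAP*

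**What the plan says.** SAP 5.1.3 and Protocol 5.2.3 define the three endpoints in the same form. For vital signs the SAP has: "Percentage of subjects who meet the markedly abnormal criteria for vital sign measurements at least once postdose".

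SAP 7.12.2 to 7.12.4 turn these into counts. For laboratory tests: "The number and percentage of subjects with at least 1 postdose markedly abnormal laboratory test result will be summarized". For vital signs: "The number and percentage of subjects with at least 1 postdose markedly abnormal vital signs measurement will be summarized". The ECG sentence is built the same way. None of the three mentions the baseline value.

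The criteria in SAP Appendices A, B and D are fixed cut-offs, for example a low ECG heart rate of "< 50 beats per minute". The exception is one branch of the QTcB and QTcF criteria, which needs a rise of at least 30 msec from baseline together with a value of at least 450 msec.

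On timing, SAP 7.12.2 says: "Only observations within 3 days of the last dose of study drug will be included in the tables". SAP 7.12.3 and 7.12.4 carry nearly the same sentence without the words for last dose. Each of the three sections then says of MAVs: "All observations, including ones at unscheduled visits, will be included in the MAV evaluation and summaries".

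**The concern.** A postdose count that ignores baseline mixes two groups: subjects who crossed a limit on treatment, and subjects who were already beyond it and stayed there. Randomisation should spread the second group about evenly, so it adds a similar share to every arm and pulls the arms together. With 52 subjects per dose, 78 on placebo and no planned test, the printed percentages are all that the reader has to compare.

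Entry criteria do not close the gap for every parameter. Protocol 7.2, item 24, says that "nonclinically significant sinus bradycardia and sinus tachycardia will not be considered significant medical illnesses", and gives no rate, while the MAV limits for pulse and heart rate are below 50 and above 120. No numeric entry limit exists for temperature, PR, QRS, uncorrected QT, GGT or CPK.

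The timing sentences raise a separate problem. Off-drug measurements will exist, and two programmers following the same SAP section could report different numbers for a named endpoint.

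**Working it through.** **Plan's own figure.** The documents give no expected MAV rate, and no power or precision figure for these endpoints. The stated power of at least 82% concerns the primary endpoint and has no bearing here.

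**Which parameters are exposed**

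| Parameter | Entry limit (Protocol 7.2) | MAV limit (SAP appendices) |
|---|---|---|
| ALT, AST | excluded if >2 × ULN | >3 × ULN |
| Bilirubin, creatinine | excluded if >1.5 × ULN (Gilbert exception for bilirubin) | >2.0 mg/dL each |
| QTcF | excluded if >450 (men) or >470 msec (women) | ≥500, or ≥30 rise and ≥450 msec |
| High blood pressure | excluded if >160 systolic or >95 diastolic | >180 or >110 |
| Pulse, heart rate | no number | <50 or >120 |
| Temperature | no number | <35.6 or >37.7 °C |
| PR, QRS, uncorrected QT | no number | PR ≤80 or ≥200; QRS ≤80 or ≥180; QT ≤300 or ≥460 msec |
| GGT, CPK | no number | >3 × ULN; >5 × ULN |

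The first four rows are largely protected. The last four are not.

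**How dilution works.** Let b be the share of subjects with a baseline MAV that is seen again postdose, equal in all arms, and x the new-onset risk in the rest. Then

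P(counted) = b + (1 − b)x.

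The risk difference is therefore multiplied by (1 − b), while the risk ratio moves toward 1 faster. Both b and x below are assumptions.

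| b | x = 2% vs 10%: counted | difference, ratio | x = 5% vs 15%: counted | difference, ratio |
|---|---|---|---|---|
| 0 | 2.0% vs 10.0% | 8.0, 5.00 | 5.0% vs 15.0% | 10.0, 3.00 |
| 2% | 4.0% vs 11.8% | 7.8, 2.98 | 6.9% vs 16.7% | 9.8, 2.42 |
| 5% | 6.9% vs 14.5% | 7.6, 2.10 | 9.8% vs 19.3% | 9.5, 1.97 |
| 10% | 11.8% vs 19.0% | 7.2, 1.61 | 14.5% vs 23.5% | 9.0, 1.62 |
| 20% | 21.6% vs 28.0% | 6.4, 1.30 | 24.0% vs 32.0% | 8.0, 1.33 |

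In subjects, at b = 10% and x = 2% vs 10%:
- Placebo: 0.118 × 78 = 9.2 counted, of whom 0.10 × 78 = 7.8 were abnormal before dosing.
- One dose: 0.190 × 52 = 9.9 counted, of whom 0.10 × 52 = 5.2 were abnormal before dosing.
- If every baseline MAV recurs, a new-onset line would show 1.4 of 70.2 against 4.7 of 46.8, which is 2% against 10%.

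**Off-drug records (Protocol 6.1, Table 9.a and Appendix A)**
- Vital signs are taken at Visit 11 in all subjects, 10 to 14 days after the last dose. That is 1 of 8 scheduled postdose visits (Visits 4 to 11).
- Visit 11 chemistry and hematology are conditional on clinically significant results at Day 84/ET.
- No ECG is scheduled at Visit 11, and Day 84/ET is the only scheduled postbaseline ECG. Early-termination procedures other than the rating scales are done even more than 1 week after the last dose, so a late ECG is kept under one sentence and dropped under the other.

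Size, again by assumption: at an independent 2% risk per visit, the vital sign count is 1 − 0.98^7 = 13.2% without Visit 11 and 1 − 0.98^8 = 14.9% with it. If abnormalities persist within a subject, Visit 11 adds less than these 1.7 points. If off-drug values add a 3% risk in every arm and b = 0, then 2% vs 10% becomes 1 − 0.98 × 0.97 = 4.9% vs 1 − 0.90 × 0.97 = 12.7%, a difference of 7.8 points and a ratio of 2.57.

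**The case against.** The other side has several good points.

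- **Off-drug values may already be excluded.** The MAVs are to be tabulated, and the 3-day rule covers the tables. In SAP 7.12.2 it is a stand-alone paragraph ahead of the MAV text. The sentence on all observations may only contrast scheduled with unscheduled visits, as the ECG section suggests by limiting its descriptive summary to scheduled measurements. A reader might infer that the SAP definitely counts Visit 11 vital signs. The documents do not settle that; they support only a conflict.
- **A baseline value is not itself counted.** Only an abnormality seen again postdose is. This stands and sets the limit of the point.
- **Baseline is not wholly ignored.** One QTc branch needs a change, and the title of Appendix B speaks of changes from baseline, although its cut-offs are absolute. Protocol 7.2, item 27, also excludes laboratory values judged clinically significant at screening, which could reach GGT and CPK. Exposure is therefore uneven.
- **Baseline status can be traced.** Change-from-baseline summaries, full listings for any subject with a MAV, and an ECG shift table are planned. But the shift table covers overall interpretation only, and neither means nor listings give a by-arm percentage of new MAVs.
- **An inclusive count is a recognised conservative choice, and it is the protocol's endpoint.** This stands, and is a reason to add to the count, not replace it.
- **Off-drug values may still reflect treatment.** True soon after stopping, so they should be shown, not discarded.

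The suicidality endpoint makes a tempting comparison, since it is worded "Percentage of subjects with treatment-emergent suicidal ideation or suicidal behavior". The contrast rests on wording alone: SAP 7.12.5 gives no treatment-emergent derivation for it either.

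**Conclusion.** The point holds in a limited form. The three MAV summaries count persisting baseline abnormalities in every arm, and this shrinks any drug-placebo contrast. The direction follows from the definition if such abnormalities are balanced across arms. The size does not follow from anything in the documents: across the assumed range, b = 2% to 20% takes 2% to 20% off the risk difference, and takes a risk ratio of 5.0 to between 2.98 and 1.30. These figures assume equal b in all arms.

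A reader might go further and infer that a real safety signal would be missed or that power is lost. The documents do not support that. Laboratory and ECG summaries exclude inferential statistics, vital signs are summarised descriptively, no source gives baseline MAV rates, and the loss on the risk difference scale is modest.

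The two timing rules are a genuine internal conflict. It mainly affects vital signs, with occasional late early-termination records for ECG and laboratory tests. Overall this is a cheap improvement to the safety tables. It does not touch the primary analysis.

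**What to change.** In SAP 7.12.2 to 7.12.4:

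1. Keep the protocol-defined count of subjects with at least one postdose MAV.
2. Add, by arm, a treatment-emergent MAV line: subjects with no MAV for that parameter and direction at Day 1 predose who have one postdose, with the denominator restricted to subjects without that baseline MAV. Show subjects abnormal at baseline in a separate column. For QTc, judge baseline status on the absolute limits, since the change branch cannot be met at baseline.
3. State that the 3-day window after the last dose applies to the MAV counts and that unscheduled values inside it are included. Use the same wording in all three sections.
4. Show later values separately, including Visit 11 vital signs and late early-termination records.

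The cost is SAP wording and one extra line or column per MAV table. Vital signs, laboratory tests and ECG are already scheduled on Day 1, so no new data are needed and the protocol endpoint is unchanged. The new line does not capture worsening in subjects already abnormal at baseline; the retained count and the listings still show them.
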